Participants may need to discontinue treatments prior to the end of the 12-week treatment period (e.g., following an adverse reaction to duloxetine; see Section 10.2.1 for list of reasons). Participants needing to discontinue first period treatment will be switched to a randomly selected second treatment at Visit 1. Participants needing to discontinue second period treatment will remain in the study and undergo all future assessments for which they are eligible.

The study will enroll approximately 820 participants in order to randomize approximately 740 individuals and to have approximately 630 completers (i.e., 15% dropout rate after randomization assumed). Assuming dropout occurs uniformly across study interventions, the sample size of 740 randomized will result in having approximately 80% probability of estimating a DTR within 90% of the optimal DTR based on the study's primary endpoint. See Section 13.2 for additional details on sample size needs for precision medicine objectives, including assumptions regarding intervention effect sizes.

The interventions under evaluation are evidence-based, with established efficacy and are standard of care. Therefore, we do not expect they will pose safety risks such that these interventions need to be stopped before the end of the study. Safety data and adverse events will be monitored. These data will be reported to and reviewed by a Data Safety and Monitoring Board. Generally, this trial will inform a precision medicine approach to the treatment of chronic low-back pain and therefore we are not planning interim analyses for futility or efficacy in order to maintain sufficient power for the precision medicine analyses. Blinding is not feasible for study participants or staff involved in the delivery of interventions. Investigators involved in the analysis of study data will be blinded to treatment assignment.

The study timeline involves approximately 9 months of participant enrollment across 12 sites for a total of 820 enrolled. Sites will enroll ~7 participants per month. We anticipate that ~90% of participants who consent at the Enrollment Visit will be randomized at the end of the 2-week run-in at Visit 0 and that 85% of randomized participants will complete all study activities. The total study duration for all participants is 38 weeks. To minimize participant burden, where possible, data will be collected remotely.

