Participants randomized to the duloxetine arm will review the dosing schedule for the medication and safety information for the medication at the baseline visit with the study coordinator. At the baseline visit a physical assessment will be performed. Certain sections must be completed by a licensed medical professional (e.g., MD, DO, FNP, PA, PT). Drug contraindications (including allergy to duloxetine, concomitant antidepressant use, concomitant tramadol use, liver disease, kidney disease, concomitant of St. John's wort use) will be reviewed with the participant. Participants reporting a history of bipolar disorder, manic episodes, or suicide attempts will not be randomized to the duloxetine intervention arm. Participants will also be counseled on seeking emergency help if suicidal ideation occurs while on duloxetine.

Participants will be treated with duloxetine for 12 weeks during the active treatment phase. At the time of randomization, the approved drug pharmacy at each study site will dispense between 185 and 192 duloxetine 30 mg capsules and provide to participants. This will ensure enough to maintain up to a 60 mg dosage through the 12-week intervention phase and to taper the dose in through the 14th week if needed.

Duloxetine will be started at 30 mg, orally once per day in the morning for the first 7 days. Study staff will conduct an assessment via phone on day 7 (or next business day if falls on a weekend) of the intervention phase with participants newly randomized to duloxetine (i.e., day 7 of either the first or second intervention period). Study staff will document in the case response forms any adverse events and safety concerns the participants may have.

At the Day 7 assessment:

Participants tolerating the medication with no side effects (e.g. nausea) will be escalated to 60 mg (two 30 mg capsules) by mouth once per day in the morning.

Participants tolerating the medication with mild side effects will have the option to stay at 30 mg or discontinue the medication.

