Participants not tolerating the medication will be instructed to discontinue duloxetine. Participants in the first period intervention will be instructed to discontinue treatment until the next randomization point (Visit 1) at which time they will be randomized to a non-duloxetine second period intervention. Participants randomized to duloxetine in the second period intervention and not tolerating the medication will be instructed to discontinue duloxetine until their final follow-up of outcomes 24 weeks post baseline (Visit 2).

All participants will be provided with the site phone number and instructed to call if they have new or worsening side effects. If any safety or adverse events occur, the medication will be discontinued.

All participants will be assessed at the midpoint of the intervention treatment period (i.e., either Week 6 or Week 18) for tolerance, adverse events, and response. At the midpoint phone call:

Participants tolerating the medication with no side effects will be instructed to increase to 60mg/day (if currently taking 30mg/day) or remain on their current dosage (if currently taking 60mg/day).

Participants tolerating the medication with mild side effects (e.g. nausea) will be given the option of continuing their current dosage (30mg/day or 60mg/day), reducing their dosage (from 60mg/day to 30mg/day), or tapering off their current dosage (if currently taking 30mg/day).

Participants not tolerating the medication will be instructed to taper off the medication.

During the Week 18 call, participants will be reminded that their study treatment period is ending in six weeks. If they are tolerating the study medication and would like to continue duloxetine after the end of the treatment period, they should schedule an appointment with their provider to discuss continuing their duloxetine treatment outside of the study, in order to avoid a lapse in medication.

Tapering instructions:

The standard tapering period is up to two weeks. The following instructions will be provided to participants when they end their duloxetine treatment at either Visit 1 or Visit 2, or during the Week 6

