^{*} Patients initially randomized to ESC with 12-week PGIC scores of 3-7 will be randomized to augmentation and not switching.

Table 10.1 provides a list of all possible augmentations (combinations of the initial treatment with a second study intervention) and treatment switches for each of the initial treatment assignments. This randomization will be performed within initial treatment by using the minimization method^{62,63} to achieve study-wide balance across treatments. Over the course of the study, the number and proportion of participants assigned to augmentation and switching overall, blinded to initial treatment assignment, will be monitored. If the proportions in each group differ meaningfully from the underlying assumptions used in the estimation of sample size, the proportion randomized to augment vs switch within Group 3 will be adapted to maintain power.

All Potential Second Stage All Potential Sw		All Potential Switches to Second
First Stage Treatment	Augmentations	Treatments
ESC	ESC + ACT	N/A
	ESC + Duloxetine	
	ESC + EBEM	
ACT	ESC + ACT	ESC
	ACT + Duloxetine	Duloxetine
	ACT + EBEM	EBEM
Duloxetine	ESC + Duloxetine	ESC
	ACT + Duloxetine	ACT

	Duloxetine + EBEM	EBEM
EBEM	ESC + EBEM	ESC
	ACT + EBEM	ACT
	Duloxetine + EBEM	Duloxetine

Participants who must discontinue first-stage treatment early, regardless of their PGIC or PEG score, will be randomized to switch to a second treatment. These individuals will discontinue treatment and will be randomized to switch to a second-line treatment 12 weeks post baseline (Visit 1).

Randomization will be performed using the Carolina Data Acquisition and Reporting Tool (CDART), developed by the Collaborative Studies Coordinating Center at the University of North Carolina. CDART is designed and implemented as a centrally hosted, web-based, customizable and scalable data management system. Randomization algorithms will be developed by a biostatistician and custom-written in Java, which provides a full set of libraries and tools capable of complex algorithm implementation. This data management system will provide a means for implementing treatment allocation protocols, masking allocation of future participants, and for study staff to obtain allocation information immediately following randomization. Study staff and participants will not be blinded to treatment allocation given the nature of the interventions. Study investigators and staff involved in data analysis will be blinded to assignment.

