11. STUDY INTERVENTION DISCONTINUATION AND PARTICIPANT DISCONTINUATION/WITHDRAWAL

11.1. DISCONTINUATION OF STUDY INTERVENTION

Early discontinuation of treatment is anticipated to be rare. Examples include a broken leg, precluding continuation of EBEM, or adverse reaction to duloxetine, necessitating discontinuation of duloxetine treatment.

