12.3. ADVERSE EVENTS AND SERIOUS ADVERSE EVENTS

12.3.1. DEFINITION OF ADVERSE EVENTS (AE)

An adverse event (AE) is defined as any untoward or unfavorable medical occurrence in a human patient or research subject, including any abnormal sign (for example, abnormal physical assessment or laboratory finding), symptom, or disease, temporally associated with the subject's participation in the research, whether or not considered related to the subject's participation in the research. Adverse events occurring after the participant provides informed consent will be recorded.

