We expect missing data to be minimal because of study procedures discussed previously to enhance retention such as incentives, incorporation of patient stakeholder feedback in the development of study materials, and efforts to minimize participant burden. In addition, there will be ongoing participant engagement through a study website, contact with research staff and regular patient engagement efforts. Finally, protocols for discontinuation of study treatment that are not tolerated are planned to enhance retention. We will continue to follow all participants until the end of the study and will utilize alternative forms of data collection for those who do not attend planned study visits (e.g., telephone administration or online data collection). Despite these efforts, missing data will arise and, as needed and appropriate, will be addressed using non-parametric multiple imputation procedures. Sensitivity analyses will be presented in detail as part of the SAP.

13.4.2.ANALYSIS OF THE PRIMARY EFFICACY ENDPOINT(S)

Complete details will be provided in the formal Statistical Analysis Plan for the study.

13.4.3.ANALYSIS OF THE SECONDARY ENDPOINT(S)

Complete details will be provided in the formal Statistical Analysis Plan for the study.

13.4.4.SAFETY ANALYSES

No safety analyses are planned other than descriptive summaries and data listings of reported adverse events.

13.4.5.BASELINE DESCRIPTIVE STATISTICS

Complete details will be provided in the formal Statistical Analysis Plan for the study.

13.4.6.PLANNED INTERIM ANALYSES

No interim analyses are planned for the study. Adaptation to the design, *i.e.* the second stage randomization probabilities, is planned and details will be included in a future Statistical Analysis Plan. Briefly, overall proportions of participants assigned to augment or switch will be monitored. If proportions deviate meaningfully from assumptions, we will consider shifting randomization probabilities within Group 3 (*e.g.*, from 50/50 to 60/40 augment/switch).

13.4.7.SUB-GROUP ANALYSES

N/A

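### Protocol Section 10.2.1 stops duloxetine for any adverse event, contradicting its own options for mild side effects and, read literally, forcing Stage 1 responders to switch

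*Protocol*

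**What the plan says.** Protocol Section 10.2.1 contains three instructions that bear on a participant with a side effect.

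- **Day 7 call:** "Participants tolerating the medication with mild side effects will have the option to stay at 30 mg or discontinue the medication".
- **Midpoint call (Week 6 or 18):** participants with mild side effects, nausea being the example given, "will be given the option of continuing their current dosage (30mg/day or 60mg/day", or may reduce the dose or taper off.
- **Between these two rules**, directly after participants are told to phone the site about side effects: "If any safety or adverse events occur, the medication will be discontinued".

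Section 12.3.1 defines an adverse event as "any untoward or unfavorable medical occurrence in a human patient or research subject" that is temporally associated with participation, and does not require relatedness. The severity scale in Section 12.3.3 starts at mild.

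Two sections set out what follows an early stop in Stage 1. Section 7.1, which points to Section 10.2.1 for the reasons, says: "Participants needing to discontinue first period treatment will be switched to a randomly selected second treatment at Visit 1". Section 10.4.4 covers "Participants who must discontinue first-stage treatment early, regardless of their PGIC or PEG score" and randomises them to switch.

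**The concern.** The third instruction is mandatory and has no qualifier for severity, seriousness, relatedness or tolerability. With the Protocol's own definition of an adverse event, it requires stopping in the very situations where the other two rules allow continuing.

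Two things are at stake. A participant could lose a drug that is tolerated and may be working. In Stage 1, the stop would also replace the response-based Stage 2 assignment with a forced switch, so a responder who should maintain or augment would be switched for a reason unrelated to response. The Stage 2 action and the participant's history are the raw material for estimating the dynamic treatment regime (Section 13.1).

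**Working it through.** The point rests on text, and the plan gives no figure to reproduce. The check sets the rules side by side and follows one case through them.

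**Step 1. Is mild nausea an adverse event?** Yes. Section 12.3.1 covers any untoward occurrence, related or not, and Section 12.3.3 has a mild grade.

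**Step 2. What happens to that participant's duloxetine?**

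| Protocol text | Action for mild, tolerated nausea |
|---|---|
| Section 5.2.1 (duloxetine risks) | Dose may still rise to 60 mg after seven days |
| Section 10.2.1, Day 7 | Stay at 30 mg or stop, by choice |
| Section 10.2.1, midpoint | Continue, reduce or taper off, by choice |
| Section 10.2.1, disputed sentence | Stop |

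The last row conflicts with the other three. Confining the sentence to unscheduled calls does not help: someone phoning in Week 3 with mild nausea would have to stop, while someone reporting the same nausea at Week 6 could continue.

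**Step 3. What does a Stage 1 stop do to the Stage 2 assignment?** The groups come from Section 10.4.4. Section 13.4.6 illustrates a possible shift in the Group 3 split as "from 50/50 to 60/40 augment/switch", so the nominal starting split is taken as 50/50.

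| Group | Normal Stage 2 action | Action after a literal stop | Share whose action changes |
|---|---|---|---|
| 1 (PGIC 1-2, PEG <4) | Maintain | Switch | 100% |
| 2 (PGIC 1-2, PEG ≥4) | Augment | Switch | 100% |
| 3 (PGIC 3-4) | Augment or switch, nominally 50/50 | Switch | 50% |
| 4 (PGIC 5-7) | Switch | Switch | 0% |

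These shares apply to participants with a tolerated event who are stopped under the literal rule. Those who do not tolerate the drug switch under either reading.

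**Step 4. How many could be affected?** The documents give no duloxetine adverse-event rate and no split by response group, so no count is possible. Only participants assigned duloxetine in Stage 1 could be force-switched by this sentence. The baseline table in the SAP gives 198 of 805: 198 / 805 = 24.6%. That ceiling is loose, because it still includes participants with no event, those who did not tolerate the drug, Group 4, and those who never reached Stage 2.

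**Step 5. What was intended?** Sections 4.1, 5.2.3, 5.2.4 and 12.2 all use inability to tolerate treatment as the standard. Section 11.1 adds: "Early discontinuation of treatment is anticipated to be rare". That expectation does not fit a stop for every adverse event. The SAP's Trial/Study Design section describes the non-response route to switching as intolerance of the initial treatment.

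**The case against.** The strongest reply is that nobody would read the sentence literally. It follows the instruction about phoning in with side effects, explicit rules for mild side effects stand on either side of it, and the rest of the Protocol and the SAP speak of intolerance. Section 5.2.2 says participants who improve may continue their treatment. Section 7.1 asks those who merely wish to stop, with PGIC below 6 and no contraindication, to carry on to Week 12. On this view it is a drafting slip with no shown consequence.

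Much of this stands. The intent is clear, and no document shows a site acting on the literal wording. The 50% for Group 3 rests on an illustrative split that the Protocol allows to be adapted. The SAP's least squares means are by Stage 1 assignment in all randomised participants, regardless of adherence, and are not touched; the regime analysis lies outside this SAP. Some relevant data are already planned: adverse events at Day 7, tolerance checks at midpoints and visits, discontinuation counts for the DSMB, and non-completion reasons in SAP Appendix 1.

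It does not remove the conflict. No text limits the sentence, and Section 7.1 sends readers to this section for the reasons that lead to a forced switch. The passages in Sections 5.2.2 and 7.1 do not govern a mandatory safety stop. Section 14.1.14 counts any noncompliance with the Protocol as a deviation, so a site that keeps a mildly nauseated participant on the drug obeys one rule and breaks another. The planned data may not isolate why the drug was stopped: the switch groups in SAP Appendix 1 are labelled by low or poor response, with none for early discontinuation.

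**Conclusion.** The concern holds: the sentence is wrong as written. It contradicts the Day 7 and midpoint rules in its own section. If followed, it would change the Stage 2 action for all affected participants in Groups 1 and 2 and for the nominal half of Group 3 that would have been augmented.

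The textual conflict is certain. The consequence depends on a literal reading that the documents do not show was applied, and its frequency cannot be estimated beyond the loose ceiling of 198 participants. Sample size, analysis population and the SAP's planned estimates are unaffected. This is an operative stopping instruction that should be corrected, not a flaw that invalidates the planned outcome analysis.

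**What to change.** Replace the sentence in Section 10.2.1 with wording such as: *If an adverse event is not tolerated, or the investigator judges that it requires stopping, duloxetine will be discontinued; mild, tolerated side effects are handled under the Day 7 and midpoint options.*

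Use the same criterion, intolerance or investigator judgement, to define who has to discontinue early in Sections 7.1 and 10.4.4. This brings both into line with the SAP's description.

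The text change costs one sentence and one shared definition. It cannot alter assignments already made: the SAP reports 805 participants randomised to Stage 1 and 683 to Stage 2. For them, record the reason for each Stage 1 duloxetine stop and each forced switch, so that the regime analysis can identify Stage 2 assignments not driven by response.

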10.2.3. FORMULATION, APPEARANCE, PACKAGING, AND LABELING

Duloxetine hydrochloride is a selective serotonin and norepinephrine reuptake inhibitor (SSNRI) for oral administration. Its chemical designation is (+)-(S)-N-methyl- γ -(1-naphthyloxy)-2-thiophenepropylamine hydrochloride. The empirical formula is C18H19NOS0-HCl, which corresponds to a molecular weight of 333.88. Duloxetine hydrochloride is a white to slightly brownish white solid, which is slightly soluble in water.

10.2.4.PRODUCT STORAGE AND STABILITY

Medications will be procured from the approved drug pharmacy at each site to retain a supply to recruit at least 5 participants at a given time. Temperature in the storage room must be managed between 20 - 25°c (68-77°F); excursions permitted to 15-30°C (59-86°F) – per package insert. Medications may also be mailed to participant directly in the event of dispensing challenges (for example as related to the COVID pandemic). Sites must follow the guidelines outlined the Duloxetine Pharmacy Manual for mailing the study medication.

10.2.5.PREPARATION

30 mg capsule

10.2.6.STUDY INTERVENTION COMPLIANCE

Compliance with study protocol will be assessed by participant report and pill count. Participants will be required to return remaining medications to the study site at the time of their next in-clinic study visit (Visit 1 or Visit 2). Unused pills will be counted and documented at the site for accountability. At sites that mail the study medication directly to participants, these participants may be permitted to retain medication previously dispensed during Visit 0 if the medication is needed to ensure a medically appropriate transition. In these cases, unused study medication must be returned at Visit 2, instead of Visit 1, under certain conditions as described in the Duloxetine Pharmacy Manual.

Adherence to the intervention will be assessed in terms of 1) missed doses as reported by the participant and 2) number of capsules left in the returned medication bottle.

10.3. STUDY INTERVENTION(S) ADMINISTRATION: ENHANCED SELF-CARE

The content of the Enhanced Self-Care intervention is based on interventions which are currently available as part of many clinical practices but is formatted and structured in a manner that will provide multiple modules over the intervention period. The intervention is considered 'enhanced' in that most individuals with chronic pain do not receive an educational and self-care package. It is self-care given there will be no therapist associated with the delivery of these educational materials. The intervention will be provided digitally via multiple modules for self-administration over a period of 12 weeks. Each module will consist of evidence-based cognitive-behavioral self-management skills for pain. While all content is available to participants at all times, automated weekly email or text messaging will guide participants to specific content. Much of the material is derived from the current University of Michigan online self-management program called PainGuide.

PainGuide (https://PainGuide.com) is an educational website promoting the use of cognitive and behavioral self-management skills for chronic pain that is accessible online or by smartphone. PainGuide offers (A) education about pain, pain mechanisms, types of pain including chronic overlapping pain conditions (COPCs), and education about a wide variety of professionally administered pain treatments, (B) rationale and resources for using a variety of self-management approaches for pain, (C) a system for monitoring symptoms and self-management activities and (D) external resources supporting pain self-management. https://painge.com/supporting-pain-self-management-54-57 Multi-media is used in communicating content including videos, text, audio files, apps, and downloadable worksheets. PainGuide is an expanded version of its predecessor FibroGuide, a similar digital pain self-management program with efficacy supported by clinical trials. For the purposes of the proposed study, PainGuide has been adapted to the needs of patients with chronic low-back pain.

The Enhanced Self Care intervention arm will be comprised of three major components delivered via a single platform:

- Behavioral Self-Management

 Established education and cognitive-behavior based self-management skills training and symptoms monitoring.
- Walking Program a new module contained within PainGuide that offers a structured walking program that uses Fitbit devices for monitoring walking (e.g., Steps).
- Personalization and Engagement ESC uses weekly automated email or text messaging to
 encourage engagement and to personalize the self-management content to be highlighted each
 week based upon participants' baseline surveys.

For this study, a customized version of PainGuide will be used. This version of the self-management website will include curated education and content targeted to a chronic low-back pain population. Two new modules have been added: a Walking Program utilizing Fitbit activity trackers for feedback and an over-the-counter (OTC) treatment module (e.g., NSAIDs and topical analgesics). The walking program will utilize Fitbit step tracking to allow participants to monitor their walking progress, while the OTC medication content will be educational in nature.

10.3.1.DOSING AND ADMINISTRATION

During the baseline visit, participants will be given a link for obtaining access to the version of PainGuide designed for this study. Access to this link will be provided after randomization and will require a username and password supplied by the study staff. Study staff will help orient the participant to the navigation of the site and will aid with login, password creation, and instruct participants to watch the overview sections on chronic low-back pain and the rationale for self-management of pain (Education). Study participants will be instructed to use this program for a period of 12 weeks. Though participants can choose to self-explore the material, there will be specific instructions delivered via text message or email that will direct participants to try the first few modules in a prescribed order: (1) Educational sections ("What is Pain" "Pain Mechanisms", and "Approaches to Pain Management," (2) Goal setting, (3) the Fitbit Walking program, and (4) OTC analgesics.

After the first four modules, email or text messages will be used to make personalized recommendations for accessing additional modules based upon identified problems from the baseline assessment using the PROMIS-29+2. For example, if sleep is identified as a problem at baseline, then the sleep module would be recommended for that individual. All materials will be available to the participant. This will allow participants to return to the materials for reinforcement or to access additional information not previously reviewed.

Most of the PainGuide modules focus on self-care, education and aerobic exercise (walking program). The PainGuide's educational module on medication has been adapted for BEST to provide a more detailed discussion of the use of self-administered over-the-counter (OTC) medications for chronic low-back pain. The medication module focuses on NSAIDs, which have been demonstrated to be an effective intervention in numerous cLBP trials and systematic reviews. Most of the discussion will be on NSAID oral medications such as ibuprofen and naproxen and the importance of consistent dosing. However, these medications are not tolerated by all individuals, and oral NSAIDs are contra-indicated for some cLBP patients, such as those with a history of gastrointestinal bleeding or who take oral anti-coagulants. Materials will stress the importance of the participant talking with their primary care or pain management provider in such circumstances. The module will also provide information on other OTC preparations such as oral acetaminophen, topical lidocaine or topical diclofenac.

The BEST trial's walking program module will build on PainGuide's pacing and self-care modules. Specifically, this module will provide guidance on the importance of aerobic exercise for cLBP as well as specific self-monitoring, goal-setting, and problem-solving education appropriate for cLBP patients. The module will provide strategies to counter maladaptive pain beliefs, especially fear avoidance regarding movement. All participants will be given a web-connected wearable device, Fitbit, to assist in monitoring their step count (a metric of functional status).

Participants will continue to have access to all of PainGuide modules throughout the trial. Use of the website will be captured passively with website utilization metrics. The online platform will also provide the participants tools to track their symptoms.

The Enhanced Self Care arm will be delivered via online self-management modules:

- Week 1: Educational content
 - o What is Pain
 - Pain Mechanisms
 - Approaches to Pain Management
- Week 2: Goal setting
- Week 3: Fitbit walking program
- Week 4: OTC analgesics

 Weeks 5-12: Personalized recommendations (based on baseline, e.g., PROMIS 29+2, modules: (e.g., Sleep, Mood, Reframing)

ESC Protocol for Second Randomization Period

Participants randomized to continue receiving ESC in the second period intervention will receive personalized recommendations based on the most recently completed PROMIS 29+2.

10.3.2.ACQUISITION AND ACCOUNTABILITY

PainGuide is hosted centrally on a University of Michigan Server. Study staff at each participating site will be given the ability to establish personal accounts for each participant who is randomized to the ESC arm of the study.

10.3.3.STUDY INTERVENTION COMPLIANCE

Adherence to the intervention will be assessed in terms of 1) which modules were accessed by the participant over the course of the intervention period, 2) how long the participant spent on each module, 3) a questionnaire asking participants to provide feedback on their experience with the materials, and 4) number of days with login/activity.

